4.3 Safety Endpoint

The safety endpoint for this study is adverse event (AE). All AEs will be captured at each study visit during treatment and follow-up visits regardless of causality or severity.

Defined in the study protocol, an AE is any untoward medical occurrence, unintended disease or injury, or untoward clinical signs (including clinically significant abnormal laboratory findings) in subjects, whether or not related to the study product. This definition includes adverse event(s):

- Related to the study product or the comparator,
- Related to the study procedures involved,
- Resulting from user error or from intentional misuse of the study product.

5. GENERAL STATISTICAL CONSIDERATIONS

5.1 Scope of Abbreviated Analysis

All analyses described in this abbreviated SAP will be based on the available data for all enrolled subjects. The scope of analyses will include:

- General Analysis: Enrollment, disposition, informed consent, baseline demographics and characteristics.
- Analysis for primary endpoint – Primary effectiveness analysis.
- Analysis of safety measures.

5.2 Sample Size and Power

Per the protocol, at the time of the trial design,

“A 35% rate of SSC is projected for the SOC arm, which is consistent with the clinical experience of the Investigators. Based on the primary endpoint of incidence rate of SSC, Fisher’s exact test with a two-sided significance level $\alpha = 0.05$ will have approximately 80% power to detect the difference between an incidence rate of 35% in the SOC arm and an incidence rate of 8.75% in the Customizable arm (a 75% reduction) when the sample size in each arm is 44. To account for possible Subject replacement, the sample will be increased by up to 15% for a maximum total of 102 Subjects (51 in each treatment arm).”

The study was terminated early before it reached the final planned sample size of 102 subjects. The study enrollment was stopped on Friday, June 30, 2017. The decision of early termination was made after the interim data review described in Section 10 of this document. A total of 71 subjects (36 in Customizable™, 35 in SOC) were enrolled in this study.

5.3 Analysis Populations

The following subject populations for this clinical study are:

Safety Population – The Safety population will consist of all subjects who are randomized and do not withdraw before the attempt to apply the assigned treatment with Customizable™ or SOC surgical incision dressing regardless of its duration. Subject data will be analyzed in the arm to which they were treated. All safety results for this study will be presented based on the safety population.

Intent-to-Treat (ITT) Population – The ITT population will consist of all subjects who are randomized and do not withdraw before the attempt to apply the assigned treatment with Customizable™ or SOC surgical incision dressing regardless of its duration. Subject data will be analyzed in the arm to which they were randomized. All supportive or exploratory analyses for this study will be presented based on the ITT population.

Full Analysis Population (FAS): The FAS subject population will consist of all subjects who i) met all of the pre-operative and intra-operative inclusion criteria and none of the pre-operative and intra-operative exclusion criteria, ii) have been randomized, and iii) received treatment with either Customizable™ or SOC dressing. Subjects without SSC will need to receive at least 5 days of Customizable™ or at least 1 day of SOC dressing to be included in this set and completed Day 30 (\pm 4 days). Subjects with SSC prior to Day 30 (\pm 4 days) will be included in this set regardless of length of Customizable™ or SOC dressing treatment and treatment follow up. Subject data will be analyzed in the arm to which they were randomized and treated. The primary and secondary effectiveness analyses for this study will be based on the FAS population.

Subjects having important disqualifying protocol deviations will be excluded from ITT and/or FAS based on the results from the protocol deviation review described in Section 5.4 of this document.

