10.2 Subject Populations for Analysis

There are two principle analysis populations for this clinical study:

10.2.1 Full Analysis Set (FAS) Population – The FAS subject population will consist of all Subjects who i) met all of the pre-operative and intra-operative inclusion criteria and none of the pre-operative and intra-operative exclusion criteria, ii) have been randomized, and iii) received treatment with either Customizable or SOC dressing. Subjects without SSC will need to receive at least 5 days of Customizable or at least 1 day of SOC dressing to be included in this set and completed Visit 9/Day 30 (\pm 4 days). Subjects with SSC prior to Visit 9/ Day 30 (\pm 4 days) will be included in this set regardless of length of Customizable or SOC dressing treatment and treatment follow up. Subject data will be analyzed in the arm to which they were randomized and treated. The primary and secondary effectiveness analyses for this study will be based on the FAS population.

10.2.2 Safety Population (SP) / Intent-to-Treat (ITT) – The safety population / ITT will consist of all Subjects who are randomized and do not withdraw before the attempt to apply the assigned treatment with Customizable or SOC surgical incision dressing regardless of its duration. Subject data will be analyzed in the arm to which they were randomized. All safety results and supportive analyses for this study will be presented based on the safety population.

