10.7 Deviations to the Study Protocol

All protocol deviations will be identified, recorded and presented in a protocol deviation log. Additionally, any major protocol deviations which increase Subject risk or impact clinical study endpoints will be identified and subsequently tabulated in summary tables. These may include but are not limited to improper consent of Subject, failure of Subject to meet all inclusion criteria and none of the exclusion criteria prior to randomization, and Subject noncompliance.

Any departure or deviation from the originally planned statistical methodologies will be documented and discussed in the SAP, which will include the statistical rationale for diverting from the originally planned statistical summaries and/or analyses.

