- Protocol deviations will be defined as departures from the study protocol and could potentially affect clinical results or safety conclusions. All protocol deviations will be identified and recorded. Following applicable KCI standard operating procedures, the Protocol Deviation Review Committee evaluates the protocol deviation data and identifies all important disqualifying protocol deviations. The results from the review will be imported and incorporated in the corresponding analysis. A listing for all identified protocol deviations will be presented. Subjects disqualified from ITT or FAS analysis populations may be subsequently tabulated in summary tables.

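### The SAP allows subjects with disqualifying protocol deviations to be dropped from ITT, which contradicts the ITT definition in the protocol and in the SAP itself

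*SAP*

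**What the plan says.** Protocol 10.2.2 defines a joint safety/ITT population as "all Subjects who are randomized and do not withdraw before the attempt to apply the assigned treatment", whatever the duration of treatment, analysed as randomised. SAP 5.3 splits the two populations but keeps the entry rule: "The ITT population will consist of all subjects who are randomized and do not withdraw before the attempt to apply the assigned treatment". Withdrawal before attempted application is the only post-randomisation exit in either text.

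The last paragraph of SAP 5.3 then adds: "Subjects having important disqualifying protocol deviations will be excluded from ITT and/or FAS based on the results from the protocol deviation review". SAP 5.4.1 says how this is decided: following sponsor SOPs, "the Protocol Deviation Review Committee evaluates the protocol deviation data and identifies all important disqualifying protocol deviations". On reporting, it says that "Subjects disqualified from ITT or FAS analysis populations may be subsequently tabulated in summary tables".

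Protocol 10.7 treats deviations differently: "any major protocol deviations which increase Subject risk or impact clinical study endpoints will be identified and subsequently tabulated in summary tables". Besides improper consent, its examples include "failure of Subject to meet all inclusion criteria and none of the exclusion criteria prior to randomization, and Subject noncompliance". It also says: "Any departure or deviation from the originally planned statistical methodologies will be documented and discussed in the SAP, which will include the statistical rationale".

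The FAS is primary in both documents. SAP 7.1 repeats the primary analysis in ITT as support, and SAP 9 rules out any other planned analysis.

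**The concern.** One section of the SAP gives two incompatible rules for who is in ITT. The definition admits everyone randomised for whom application was attempted. The closing paragraph lets a committee take subjects out again, on criteria that the supplied documents do not state.

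This matters because of what ITT is for here. The FAS requires eligibility and receipt of treatment. For subjects without an SSC, and only for them, it also requires a minimum treatment duration and Day 30 completion. It is therefore selected after randomisation, partly on the outcome. The protocol planned two supports for the SSC result: the ITT comparison and an optional logistic regression in ITT and FAS (10.5.1). Only the ITT repeat survives in the SAP. If eligibility failure or noncompliance were judged disqualifying for ITT, which the SAP does not settle, ITT would lose the same kinds of subject that the FAS already loses and would be a weaker check.

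The trial is open-label (SAP 2), SAP 10 prints SSC rates by arm, and the SAP states no timing or blinding for the deviation review. Few events are involved, so one discretionary exclusion can visibly move the ITT result.

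**Working it through.** **Step 1. Compare the texts.**

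| Place | Rule |
|---|---|
| Protocol 10.2.2 | ITT: randomised and not withdrawn before attempted application; no deviation exclusion |
| SAP 5.3, ITT paragraph | The same |
| SAP 5.3, last paragraph | Disqualifying deviations lead to exclusion from ITT, FAS or both |
| SAP 5.4.1 | A committee decides under SOPs; disqualification from ITT is named again |
| Protocol 10.7 | Major deviations are identified and tabulated |
| SAP 10 | All enrolled subjects enter the final analysis |
| SAP 11 | A subject given the wrong treatment stays in ITT in the randomised arm |

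ITT is named in two separate SAP sections, so its mention is unlikely to be a slip. The rule contradicts both ITT definitions. It conflicts with SAP 10, although that sentence defers to the rest of the SAP. It fits poorly with SAP 11, where a departure as serious as the wrong treatment does not remove a subject from ITT.

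**Step 2. Recover the event counts.** SAP 10 gives 17.2% of 29 (Customizable) and 3.1% of 32 (SOC) in the interim FAS data. 5/29 = 17.2% and 1/32 = 3.1%; the neighbouring counts (4/29 = 13.8%, 6/29 = 20.7%, 0/32 = 0%, 2/32 = 6.2%) do not fit. So there were 5 and 1 subjects with an SSC.

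**Step 3. Assume ITT counts.** The documents give no ITT event counts. Assumption: the same 6 subjects with events, on the enrolled denominators of SAP 5.2 (36 and 35). Test: two-sided Fisher's exact, as in SAP 7.1, with threshold 0.048.

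**Step 4. Remove one subject at a time.** Difference = Customizable rate minus SOC rate.

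| Exclusion | Customizable | SOC | Difference (points) | p |
|---|---|---|---|---|
| None | 5/36 = 13.9% | 1/35 = 2.9% | 11.0 | 0.199 |
| The SOC subject with an SSC | 5/36 = 13.9% | 0/34 = 0% | 13.9 | 0.054 |
| A Customizable subject with an SSC | 4/35 = 11.4% | 1/35 = 2.9% | 8.6 | 0.356 |
| A Customizable subject without an SSC | 5/35 = 14.3% | 1/35 = 2.9% | 11.4 | 0.198 |
| A SOC subject without an SSC | 5/36 = 13.9% | 1/34 = 2.9% | 10.9 | 0.199 |

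**Step 5. Vary the denominators.** SAP 10 speaks of 70 treated subjects. Starting from 35/35 or 36/34 instead, and taking every single exclusion again, the difference over all three starting points runs from 8.5 to 14.3 points and p from 0.054 to 0.356. None falls below 0.048, and Customizable has the higher rate in every case.

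**Step 6. Bounding case.** Removing all five Customizable subjects with an SSC gives 0/31 versus 1/35, p = 1.00. SAP 7.1 claims a benefit only if the Customizable rate is lower and p meets 0.048, so even this does not produce the claim.

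**The case against.** The strongest reply is that little turns on this. ITT is supportive, enrolment has stopped, and on the figures above the rule neither creates nor removes a superiority claim. Wording that covers ITT, FAS or both may in practice touch only the FAS. The SAP also leaves a trail: a listing of all deviations, listings of all available CRF data, and a CONSORT diagram by arm. Only the summary tabulation of disqualified subjects is optional. All of this stands, and it limits the severity. It does not remove the contradiction, because a listing shows an exclusion only after it has been made.

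Two further replies also limit what can be said. The criteria may exist in the sponsor's SOPs, so they are missing from the supplied documents and not necessarily missing altogether. And protocol 10.7 asks for a rationale when statistical methodologies change. Treating an analysis population as part of the methodology is a reasonable reading, but the protocol does not say so. A clear breach of 10.7 is therefore more than the text supports; 10.7 appears to call for a rationale that the SAP does not give.

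A reader might also infer that an undefined exclusion could decide the trial. In the interim FAS counts, 5/29 versus 1/32 gives p = 0.093, and dropping the one SOC subject with an SSC gives 5/29 versus 0/31, p = 0.022. But that difference is against Customizable, so no benefit claim follows, and it concerns the FAS rather than ITT.

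**Conclusion.** The contradiction is real and can be read directly from the two documents: SAP 5.3 and 5.4.1 permit an exclusion from ITT that neither ITT definition contains, with neither criteria nor rationale in the supplied text. It should be corrected as a low-to-moderate point about the supportive analysis.

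What can change is the apparent size and strength of an unfavourable difference. On the illustration, one exclusion moves it between about 8.5 and 14.3 points. This rests on two assumptions: that the interim rates mean 5 and 1 subjects with an SSC, and that no other ITT subject had one. Further events, for example in subjects outside the FAS or enrolled after the review, would change the figures.

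It would be wrong to infer that subjects were removed from ITT, or that the rule was written to improve the result. No document shows either.

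**What to change.** In SAP 5.3, delete *ITT and/or* from the exclusion sentence. In SAP 5.4.1, delete *ITT or* from the sentence on disqualified subjects. Add one sentence: no subject is removed from ITT for a protocol deviation. ITT is then the population of protocol 10.2.2, and the FAS remains primary.

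If the sponsor wants an exception for data that cannot be used because valid consent is lacking, that is a new rule found in neither ITT definition. The SAP should label it as such and report the subjects concerned by arm.

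The cost is two short deletions and one sentence, with no new data and no new analysis. The change does not settle the same deviation-based exclusion for the FAS, whose criteria are also not given in the supplied documents.

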5.4 Conventions, Definitions and Handling of Missing Data/Dropouts

5.4.1 General Considerations

- Summaries of continuous variables will show the number of non-missing values (n), along with mean, median, standard deviation, minimum and maximum. In general, the maximum and minimum values will be presented to the same precision as the raw data; the mean and median will be presented to one decimal place more than the raw data. The standard deviation and confidence intervals (CI) will be presented to two decimal places more than the raw data. Exceptions for number of decimal places may be made according to the data. The p-values will be presented to four decimal places. A p-value less than 0.0001 will be presented as < 0.0001 or $< .0001$.
- Listings of all available data recorded on the case report form (CRFs) will be presented. There will be no imputation of missing data, with the exception of partially missing dates.
 - Each analysis variable with partial dates will be reviewed at the time of analysis and final decision will be made at that point on the appropriate imputation strategy. All

subject listings data will be provided as recorded on the CRFs indicating the partial dates and missing data. If needed, footnote(s) for imputed dates will be added to the data listings.

- If data are missing or incomplete and the variable is used in a calculation then the derived variable will be set to missing. Similarly in the summary tables of analyses the variable will be considered missing.
- The most recent assessment prior to the Day 0 surgery or prior to the opening of the randomization envelope will be used as the baseline reference for all analyses which incorporate a baseline value.
- All end-of-study analyses will use the last recorded observation (last visit) during the study.
- All subjects enrolled in the study who received either Customizable™ or SOC will be included in the summary of safety profile.
- Protocol deviations will be defined as departures from the study protocol and could potentially affect clinical results or safety conclusions. All protocol deviations will be identified and recorded. Following applicable KCI standard operating procedures, the Protocol Deviation Review Committee evaluates the protocol deviation data and identifies all important disqualifying protocol deviations. The results from the review will be imported and incorporated in the corresponding analysis. A listing for all identified protocol deviations will be presented. Subjects disqualified from ITT or FAS analysis populations may be subsequently tabulated in summary tables.

5.4.2 Conventions/Imputations for Adverse Events

Any adverse event that started or worsened on/after the initial application of either Customizable™ or SOC will be analyzed as treatment-emergent.

If the adverse event (AE) start date has missing data (e.g., the year of the AE start date is missing, or the month of the AE start date is missing, or the day of the AE date is missing), then choose the missing components of the AE onset date and impute the AE onset date to be as close to being on/after the date of initial application of either Customizable™ or SOC as possible.

6. GENERAL STATISTICAL ANALYSES

Enrollment and subject disposition, informed consent, demographics and baseline disease characteristics will be summarized. Summary statistics will include n, mean, standard deviation, median, and range (minimum, maximum) for continuous variables, and frequencies and percentages for categorical variables.

6.1 Enrollment, Disposition

The number and percent of subjects randomized, treated, and assessed will be presented by treatment group in tabular form and a customized CONSORT diagram. The reasons for early withdrawal and discontinuation from the study will also be presented.

6.2 Demographics and Baseline Characteristics

The following subject data and characteristics will be presented by treatment group and overall:

- Clinical site
- Age , continuous
- Age by category
- Sex
- Race
- Ethnicity
- BMI kg/m²
- BMI by category
- Type of surgery
- Type of incision
- Panniculus grade
- Tranverse incision length
- Inverse incision length
- Panniculus weight
- Panniculus weight, category
- Risk factors (diabetes, immunosuppressent, current tobacco user, and vascular disease)
- Reported medical histories.

7. STATISTICAL ANALYSIS OF EFFECTIVENESS MEASURES

7.1 Primary Effectiveness Analysis

The primary endpoint will be analyzed on subjects in the Full Analysis Population. The incidence rate of SSC will be calculated for each treatment group as follows:

$$SSC\ rate = [Number\ of\ subjects\ who\ experienced\ an\ SSC] / [Full\ Analysis\ Population]$$

Subjects included in the numerator for the incidence computation must have experienced an SSC within 34 days after the initial study surgery. If a subject experiences one or more SSC events, the subject will be counted only once in the numerator. The number and percent of subjects experiencing each component of the SSC (dehiscence, superficial SSI, deep SSI, or any SSI) will also be presented.

The incidence rates of SSC results will be presented by treatment group and overall. The Fisher's Exact test with a 2-sided significant level $\alpha = 0.048$ will be used to compare the SSC incidence rates between two treatment groups. The null and alternative hypotheses are as the follows:

H₀: The Customizable™ and SOC treatment groups have equal incidence rates of SSC

$$SSC_{Customizable} = SSC_{SOC}$$

H₁: The Customizable™ and SOC treatment groups have different incidence rates of SSC

$$SSC_{Customizable} \neq SSC_{SOC}$$

If the incidence rate of SSC of Customizable™ is smaller than the incidence rate of SSC of SOC dressing (i.e. $SSC_{Customizable} < SSC_{SOC}$) and the P-value from the above Fisher's Exact test is below 0.048 (i.e. $P\text{-value} \leq 0.048$) then we conclude that the incidence rate of SSCs decreased statistically significantly in Customizable™ compared with SOC dressing in this clinical study.

As additional supportive analysis, the above analysis will be repeated based on the ITT population.

8. ANALYSIS OF SAFETY MEASURES

All subjects in the Safety Population will be evaluated for safety. Safety analyses will include summaries of adverse event rates. In general, the summary results of safety parameters will be based on descriptive statistics.

8.1 Adverse Events

All treatment emergent adverse events will be coded using MedDRA coding dictionary (Version 20.0) and analyzed. An adverse event will be considered as treatment emergent (TEAE) if the onset is any time on or after the initial study surgery, panniculectomy or incisional hernia repair, through any time post surgery.

Number and percentage of treated subjects experiencing any TEAE will be summarized by system organ class and preferred term. Summary tables will be provided of incidences for all treatment emergent adverse events, treatment-related adverse events, adverse events by maximum severity, serious adverse events, serious adverse events related to study product and adverse events that led to study discontinuation. In any given category (e.g., system organ class or preferred term) a subject will be counted only once. If a subject has the same adverse event on multiple occasions, only the one with maximum severity will be presented. The denominator for the calculation of percentages will be the number of subjects in the sub-arm of subjects being tabulated and not the number of events.

Listings providing all serious adverse events, discontinuations due to any adverse event, or deaths occurring during the course of the study will be presented by subject.

The following summary tables and listings will be presented by treatment group and overall:

- Incidence of all treatment emergent adverse events by system organ class and preferred term.
- Incidence of all serious treatment emergent adverse events by system organ class and preferred term.
- Incidence of treatment-related adverse events by system organ class and preferred term.
- Incidence of treatment-related serious adverse events by system organ class and preferred term.
- Incidence of all treatment emergent adverse events by system organ class, preferred term, and maximum severity.
- Listing of all serious treatment emergent adverse events.
- Listing of all treatment-related serious adverse events.
- Listing of discontinuations: Subjects who discontinued from study due to any treatment emergent adverse event.
- Listing of deaths: Subjects who died of any cause during study.

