1.4 Description of the Products Under Study

1.4.1. Prevena™ Customizable™ Dressing Kit

Prevena™ Customizable™ Dressing or Prevena Plus™ Customizable™ Dressing kits will be provided by KCI as the study product to be tested in this study and will be labeled as

“Investigational Use Only” per FDA requirements. Instructions for use will be provided to each site.

[figure not shown]
The contents of the kit are listed below (shown in Figure 1):

- Prevena™ Customizable™ Dressing or Prevena Plus™ Customizable™ Dressing sealing strips
- drape
- ruler
- indicator or SensaT.R.A.C.™ pad with tubing
- tubing connector for V.A.C. units (if needed)

Figure 1. Prevena™ Customizable™ Dressing Kit Contents

Prevena Plus™ Customizable™ Dressing Kit

Prevena™ Customizable™ Dressing Kit

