9.1 Definition

9.1.1 Adverse Event (AE)

Any untoward medical occurrence, unintended disease or injury, or untoward clinical signs (including clinically significant abnormal laboratory findings) in Subjects, whether or not related to the study product.

This definition includes events:

- Related to the study product or the comparator,
- Related to the study procedures involved,
- Resulting from user error or from intentional misuse of the study product.

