9.2 Classification

9.3 Causality

The Investigator will assess the causality of the AE as:

- Related to the study product: any adverse event for which there is a reasonable possibility that the study product caused the adverse event.
- Not Related to the study product: when is determined that there is no relationship between the adverse event and the use of the study product.

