9.7 Follow-Up Period for Ongoing AEs

Treatment-related AEs and SAEs which are ongoing at the final study visit, or treatment-related AEs that occur within 30 days of the final study visit, will be followed until resolution or stabilization. All other AEs will be closed at the time the Subject completes participation in the study.

10 Statistical Plan

The primary objective of the study is to compare surgical incision-related clinical outcomes in Subjects undergoing abdominal surgery for incisional hernia repair and/or functional panniculectomy when managed with Customizable as compared to SOC surgical incision dressing.

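### The open-ended TEAE window in SAP 8.1 can bring post-study events into the by-arm all-cause safety tables mainly or only from the Customizable arm

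*SAP*

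**What the plan says.** SAP 8.1 defines the TEAE window by its start only. Onset counts from the initial study surgery, "panniculectomy or incisional hernia repair, through any time post surgery". SAP 5.4.2 and Protocol 10.6 give no end date in their treatment-emergent definitions either. The SAP 8.1 incidence tables, by treatment group and overall, cover all TEAEs, serious TEAEs, treatment-related events, treatment-related SAEs and TEAEs by maximum severity.

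Collection during the study does not depend on cause. SAP 4.3 states: "All AEs will be captured at each study visit during treatment and follow-up visits regardless of causality or severity". The last scheduled visit is Day 30 (±4) (Protocol 3.1.2 and 6.9).

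After that visit the only provision is Protocol 9.7. For events with later onset it says that "treatment-related AEs that occur within 30 days of the final study visit, will be followed until resolution or stabilization". For the rest: "All other AEs will be closed at the time the Subject completes participation in the study". After a subject discontinues early, Protocol 7.2 asks for related SAEs only, for 14 days.

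Protocol 9.3 has two causality categories. One is "Related to the study product: any adverse event for which there is a reasonable possibility that the study product caused the adverse event"; the other is not related to the study product. Protocol 1.4.1 says that the Customizable dressing "kits will be provided by KCI as the study product to be tested in this study".

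**The concern.** The analysis window has no end, but the collection rule changes inside it. Up to the final visit every event is sought in both arms. After it, the protocol provides for one kind of event only, and the rating that defines that kind is worded around one arm's product. A programmer who follows SAP 8.1 literally would count any late event in the database towards the arm's incidence, so the two columns of a table headed all-cause could rest on different collection.

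The secondary endpoint analysis has been dropped (SAP 4.2) and no other analyses are planned (SAP 9), so the by-arm AE tables are the only safety comparison in the report. With 36 and 35 subjects enrolled, a few one-sided additions would be visible.

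**Working it through.** The plan gives no figure on this point to reproduce. The check is a comparison of the texts, followed by simple arithmetic.

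1. **Window against collection.** Counting (SAP 8.1): from surgery, no end. All-cause capture (SAP 4.3): at study visits, so to Day 26–34. Provision after the final visit (Protocol 9.7): treatment-related events, 30 days. By contrast, SAP 2 and SAP 7.1 close clinical outcomes and the primary endpoint at 34 days. The AE window alone is open.

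2. **Whether the late rule depends on arm.** Protocol 9.7 does not define treatment-related. The only scale an investigator has is that of 9.3, which refers to the study product. SAP 8.1 appears to use the two terms interchangeably: its text announces a summary of "serious adverse events related to study product", and the matching table is titled with treatment-related instead. Safety data are analysed by treatment received (SAP 5.3), so subjects in the SOC column received the SOC dressing. On the 9.3 scale their late events have no related category. Against this, the AE definition in Protocol 9.1.1 includes events "Related to the study product or the comparator", so a site could still report a late event that it ascribed to the SOC dressing. Hence mainly or only, not certainly only.

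3. **Length and position of the late period.** Final visit day + 30: 26 + 30 = Day 56; 30 + 30 = Day 60; 34 + 30 = Day 64. Customizable is removed on Day 5 to 7, so the late period begins at least 26 − 7 = 19 and at most 34 − 5 = 29 days after removal.

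4. **Weight of one subject.** SAP 5.2 gives 36 Customizable and 35 SOC subjects enrolled. One added Customizable subject: 1/36 = 2.8 points; two: 2/36 = 5.6 points. The Safety Population count is not stated; with 35 subjects, one adds 1/35 = 2.9 points. Each subject counts once per row, so a late event changes a row only if the subject is not already in it. In the severity table it also matters if it raises the subject's maximum.

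5. **Range under assumed rates.** The documents give no late-event rate, so these are assumptions. If 1%, 3%, 5% or 10% of Customizable subjects had their first TEAE late and related, the expected extra subjects are 36 × rate = 0.36, 1.08, 1.8 or 3.6, that is 1 to 10 points. If instead a rate r applies only to subjects free of a TEAE up to the final visit, and both arms have incidence p by then, the Customizable figure is p + (1 − p)r. With p = 40% and r = 5% this is 40 + 0.6 × 5 = 43.0%, against 40% in SOC. Over p = 20% to 60% and r = 3% to 10%, the gain runs from 0.4 × 3 = 1.2 to 0.8 × 10 = 8.0 points.

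6. **After the fix.** With the window closed at the final visit, both columns rest on the same all-cause collection and the one-sided period is 0 days.

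**The case against.** The strongest reply is that other text already bounds the data. Protocol 10.6 speaks of events recorded in the course of the study, SAP 4.3 ties capture to visits, and SAP 2 refers to 34 days. On that reading the open end is loose drafting. It shows what was probably meant, but it does not close the window: SAP 8.1 is the definition that will be programmed, and those passages conflict with it.

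Second, Protocol 9.7 is a follow-up rule. It does not say that late unrelated events go unrecorded, nor that late related ones enter the database, and Protocol 9.6.1 and 9.6.2 state no end to reporting. This stands. The stop for unrelated events is an inference from their being closed, so the bias is possible, not certain.

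Third, a reader might infer that SOC subjects cannot contribute late events at all and that the tables are biased by construction. The documents do not go that far: treatment-related is undefined in 9.7, SOC is called a treatment elsewhere, and 9.1.1 mentions the comparator.

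Fourth, a reader might take the late period's share of calendar time, 30/64 to 30/56 or 47% to 54%, as the size of the problem. It measures days, not events or bias. No visit is scheduled in that period, and first product-related events some three weeks or more after removal are likely to be few.

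Finally, a cutoff applied to every table would take real late device harms out of the treatment-related counts. It would not make those tables symmetric either, because on the 9.3 scale they are one-sided at any time. This stands and limits the fix.

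**Conclusion.** The point holds as a minor one. SAP 8.1 states an open window that spans two collection regimes, and the later regime favours events from the Customizable arm. The consequence is a possible upward bias in that arm's all-cause TEAE, SAE and severity figures, at 2.8 points per subject whose only TEAE is late, if all 36 enrolled subjects are in the Safety Population. The likely total is small, but it cannot be estimated from the documents. The conclusion assumes that sites rate late events on the 9.3 scale and that those events reach the database. The tables are descriptive (SAP 8), no test depends on them, and the primary analysis has its own 34-day limit.

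**What to change.** In SAP 8.1, give the TEAE window an end for the by-arm all-cause TEAE, SAE and maximum-severity tables: onset no later than the subject's final study visit (Day 30 ±4) or early withdrawal visit. This agrees with the 34-day window in SAP 2 and SAP 7.1. Show events with later onset in a separate listing by arm. Keep late product-related AEs and SAEs in the treatment-related tables, flagged as post-study onset, so that no device harm is dropped.

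The cost is one sentence, one listing and one flag, with no new data. The downside is that a few late events leave the all-cause comparative tables, though they remain visible in the listing and, where product-related, in the treatment-related tables.
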